## Evaluation and Clinical Outcomes After Routine Cataract Surgery with the Quatera® 700 and the Centurion® Vision System

### INTRODUCTION

Accordingly with the last report from World Health Organization (WHO) at least 2.2 billion people globally have a near or distance vision impairment and almost 94 million of those people present age-related cataract, considered the second cause of visual impairment and the main cause for reversible blindness worldwide. Characterized by the darkening and solidification of a previously transparent crystalline lens; the condition is responsible for both vision impairment and also for a decreased quality of life, due to restriction to independent living; and increased risk of body injuries, anxiety and depression levels; in individuals with non-operated cataracts.

At the early stages the cataracts can be managed by changing the prescribed glasses, however their progression is unpredictable, and sometimes changes associated with the progression could lead to rapidly increasing refractive errors, significant anisometropia and to lower visual acuity, leading to the necessity of a surgical procedure to restore the visual capacity to patients with age-related cataract.

Phacoemulsification is the most common treatment for cataract surgery in the developed countries and over the years it gained importance due to several factors: small incision, surgery performed under topical anesthesia - which reduce injection-related complications – short recovery time, low post operator induced astigmatism, and low incidence of surgical complications, when compared to the conventional surgeries.

Although phacoemulsification has fewer complications when compared to previous types of cataract surgeries, it still burdens undesirable side effects, in the form of intraoperative and/or post-operative complications. Anterior segment changes occur after phacoemulsification surgery, and corneal endothelium seems to be the most adversely affected structure with significant loss of corneal endothelial cells density and corneal thickness during cataract surgery. Corneal endothelial cell loss can be caused by the heat originated from the ultrasound, excessive irrigation, turbulence of fluid, bubble generation in the anterior chamber, and direct trauma, leading to a reduced corneal metabolism postoperatively. In severe cases, corneal decompensation may occur, following an ineffective endothelial pumping, resulting in persistent corneal edema, and decreased vision leading to subsequent corneal transplantation. Some factors act as adjuvants to increase the risk of cell damage like intraoperative phacoemulsification time, shorter eyes, and a shallow anterior segment, and because of all that it is important to perform surgery as effectively and safely as possible to avoid disrupting the delicate balance of the eye.

Corneal thickness changes after phacoemulsification can be used to assess surgically induced corneal edema and it was already observed that the degree of permanent corneal endothelial damage is related to the degree of early postoperative corneal swelling. Moderate damage of the corneal endothelium during surgery may lead to a transient increase in corneal thickness, although data about it are contradictory since some authors reported that all patients recovered preoperative values after 4 weeks, while others reported sustained increases up to 6 months or even 1 year postoperatively; however, those discrepancies may reflect inadequate measurement of central corneal thickness (ultrasonic pachymetry) and in the estimation of endothelial cell numerical density. Nowadays modern technology, such as optical low coherence reflectometry, allows more precise measurements of the central corneal thickness and published data show that a moderate decrease in the endothelial cell numerical density does not influence the central corneal thickness, if accurately determined, at various time intervals up to 1 year after surgery.

The purpose of this study is to evaluate and compare the performance of 2 different phacoemulsification systems: the Zeiss Quatera® 700 and the Centurion® Vision System, when using the optimized settings for each device, in patients undergoing routine cataract surgery.

## 1. OBJECTIVE:

The purpose of this study is to evaluate the Zeiss Quatera® 700 and compare it to the Centurion® Vision System using the optimized settings for each device in patients undergoing uneventful routine cataract surgery. Main end points include central corneal thickness at day 1 postoperatively and lens removal time (from end of rhexis to complete nucleus removal) as measured digitally by the Zeiss Surgery Optimizer and manually with a stopwatch.

## 2. STUDY DESIGN AND METHODS:

A. **Test article:** Zeiss Quatera® 700 and Alcon Centurion® Vision System

B. **Study Design:** Prospective, randomized, double-masked contra lateral eye study.

C. **Subjects:** A total of 40 subjects who met the Inclusion/Exclusion criteria will be enrolled.

### 1. Inclusion Criteria:

Subjects **MUST** fulfill the following conditions to qualify for enrollment into the trial

1. Subject is undergoing bilateral lens extraction with implantation of a posterior chamber intraocular lens.
2. Gender: Males and Females.
3. Age: 40 years or older.

4. Willing and able to provide written informed consent for participation in the study
5. Willing and able to comply with scheduled visits and other study procedures.
6. Scheduled to undergo standard cataract surgery with topical anesthesia in both eyes within 1 to 15 days between surgeries
7. Subjects requiring an IOL power in the range of +10.0 D to +30.0 D only.
8. Potential postoperative visual acuity of 0.2 logMAR (20/32 Snellen) or better in both eyes.

## 2. Exclusion Criteria:

Subjects with **ANY** of the following conditions on the eligibility exam (Visit 0) may **NOT** be enrolled into the trial.

1. Severe preoperative ocular pathology: amblyopia, rubella cataract, proliferative diabetic retinopathy, shallow anterior chamber, macular edema, retinal detachment, aniridia or iris atrophy, uveitis, history of iritis, iris neovascularization, medically uncontrolled glaucoma, microphthalmos or macrophthalmos, optic nerve atrophy, macular degeneration (with anticipated best postoperative visual acuity less than 20/30), advanced glaucomatous damage, etc.
2. Uncontrolled diabetes.
3. Use of any systemic or topical drug known to interfere with visual performance.
4. Contact lens use during the active treatment portion of the trial.
5. Any concurrent infectious/non-infectious conjunctivitis, keratitis or uveitis.
6. Clinically significant corneal dystrophy.
7. Corneal irregularities potentially affecting visual acuity: keratoconus, corneal dystrophy, corneal opacities.
8. Endothelial cell count less than 1500 cells/mm^2
9. History of chronic intraocular inflammation.
10. History of retinal detachment.
11. Femtosecond arcuates at time of surgery.
12. Femtosecond laser assisted cataract surgery in one eye only.
13. Pseudoexfoliation syndrome or any other condition that has the potential to weaken the zonules.
14. Previous intraocular surgery.
15. Previous radial keratotomy (RK).
16. Previous keratoplasty
17. Pupil abnormalities
18. Subject who may reasonably be expected to require a secondary surgical intervention at any time during the study (other than YAG capsulotomy, i.e. LASIK)
19. Anesthesia other than topical anesthesia (i.e. retrobulbar, general, etc).
20. Other ocular procedures at the time of the cataract extraction (i.e., iStent)

21. Any clinically significant, serious or severe medical or psychiatric condition that may increase the risk associated with study participation or may interfere with the interpretation of study results.
22. Participation in (or current participation) any ophthalmic investigational drug or ophthalmic device trial within the previous 30 days prior to the start date of this trial.

The principal investigator reserves the right to declare a patient ineligible or non-evaluable based on medical evidence that indicates the patient is unsuitable for the trial.

### 3. Study Procedures

#### A. Informed Consent / Subject enrollment

Potential subjects will be identified from the patients presenting at the clinic. Additionally, an ad will be placed in social media and in the practice website, if deemed necessary. Once identified as a study candidate, the patient will be asked if he/she would like to participate. The sub-investigator, study coordinator or an appropriately trained staff member will answer any and all questions and will obtain informed consent. A copy of the signed informed consent document will be given to the subject. The principal investigator will be available if the subject wants to discuss further details with him. Any testing that is part of the investigative site's standard preoperative cataract evaluation may be performed prior to the informed consent being signed, provided these tests are conducted within 90 days of surgery. The patient will understand that participation in the study, or declining to participate, will not affect his/her quality of care.

No subject will be enrolled into the study that does not meet the inclusion/exclusion criteria and does not sign the current approved informed consent document. Informed consent will be obtained prior to collecting any data for the study. The original signed documents will be maintained by the investigator as a permanent part of the subject's research records.

#### B. Surgery Procedures:

The first eye undergoing surgery will be randomized to either the Quatera® 700 or the Centurion® Vision System. The fellow eye will receive the alternate treatment. The first operative eye will be the eye with the worse cataract. If the cataract is the same in both eyes, the clinic's standard of care will be followed. The randomization list will be provided by a third-party consultant. Research staff not attending or participating in surgery will be masked to the extent possible.

### C. Study Visit Schedule and Assessments (Table 1).

#### 1. Visit Schedule: Subjects will be examined at the following intervals:

1. Visit 0: Screening and enrollment: Preoperative evaluation completed not more than eight weeks before surgery
2. Visit 1: Day of Surgery each eye
3. Visit 2: Day 1: (12 to 48 hours) after surgery each eye
4. Visit 3: Week 1: 7  $\pm$  2 days after surgery each eye
4. Visit 3: Month 1: 30  $\pm$  7 days postoperative after second eye surgery
4. Visit 4: Month 3: 90  $\pm$  15 days postoperative after second eye surgery

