### D. Measurements and evaluations

1. Visit 0: Informed consent process will be conducted at this visit. Assessments include best-corrected distance visual acuity (BCDVA, Snellen chart), manifest refraction, intraocular pressure (IOP, Goldman), corneal tomography (Pentacam), ultrasound pachymetry, specular microscopy, macular OCT, slit lamp examination including dilated fundus exam, cataract density and type (LOCS III). Any testing that is part of the site's standard of care preoperative cataract surgery evaluation may be performed prior to the informed consent being signed provided these tests are conducted within 90 days of the surgery and notation of the date performed is entered onto the CRF. The surgeon's standard pre cataract surgery treatment will be used in all his patients

First eye undergoing surgery will be randomized to Group A (Quatera 700) or B (Centurion).

2. Visit 1: The surgeon may use his preferred small incision cataract extraction technique (manual phacoemulsification or laser assisted). The same technique must be used in both eyes. The intraocular lens will be implanted in the bag. The following information will be captured the day of surgery: phaco metrics, lens removal time, duration of surgery, incision size (prior to lens implantation), estimated fluid used, lens implanted and power, target refraction for IOL power implanted, additional surgical procedures, intraoperative complications, and any device deficiencies. Additionally, the surgery will be recorded, and the videos will be analyzed digitally using the Surgery Optimizer and manually using a stopwatch. The surgeon's standard post cataract surgery treatment will be used in all patients.

3. Visit 2: monocular pinhole uncorrected visual acuity (UCVA), slit lamp examination, IOP, ultrasound pachymetry and Pentacam.
4. Visit 3: Manifest refraction, best distance corrected visual acuity (BCVA), IOP, slit lamp examination, ultrasound pachymetry, Pentacam and macular OCT.
5. Visit 4: Manifest refraction, best distance corrected visual acuity (BCVA), IOP, slit lamp examination, ultrasound pachymetry, Pentacam, macular OCT, and dilated fundus exam if deemed necessary by the investigator.
6. Visit 5: Manifest refraction, best distance corrected visual acuity (BCVA), IOP, slit lamp examination, ultrasound pachymetry, Pentacam macular OCT will be performed. Dilated fundus exam to be performed if deemed necessary by the investigator.

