All adverse events and complaints will be monitored and recorded at all study visits.

**Table 1.** Visits and Study Assessments

	Visit 0 Screening	Visit 1/1A DOS	Visit 2/2A 1-day	Visit 3/3A 1-week 7 ±2 days	Visit 4/4A 1-Month 30 ±5 days	Visit 5/5A 3-Month 90 ±15 days
Informed Consent	X					
Inclusion/Exclusion	X	X				
Demographics	X					
Past medical & ocular history	X					
Concomitant medications	X					
BCVA Snellen	X					
Pinhole uncorrected distance VA (ETDRS)			X			
Manifest refraction	X			X	X	X
Best corrected distance VA (ETDRS)				X	X	X
Intraocular Pressure (Goldman)	X		X	X	X	
Specular microscopy	X					X
Ultrasound Pachymetry	X		X	X	X	X
Pentacam	X		X	X	X	X
SLE	X		X	X	X	X

Signs of inflammation (cells and flare)	X		X	X	X	X†
Dilated fundus exam	X				X††	X††
Macular OCT	X			X	X	X
Cataract density / type (LOCS III)	X					
Phaco metrics		X				
Lens removal time		X				
Duration of surgery		X				
Incision size		X				
Surgical optimizer		X				
Estimated fluid use		X				
Adverse events	X	X	X	X	X	X

X To be performed as scheduled

† To be performed if cells and flare still present at the 1-month visit

†† To be performed as deemed necessary by the investigator.

BCVA, best corrected visual acuity

ETDRS, Early Treatment Diabetic Retinopathy Study

SLE, Slit lamp exam

OCT, Optical Coherence Tomography

LOCS, The Lens Opacities Classification System

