#### 2. Secondary Endpoints:

- a. Duration of surgery (from incision to wound hydration)
- b. Incision size (prior to intraocular lens implantation)
- c. Estimated fluid use
- d. Subjective signs of inflammation (cells and flare) at day 1, 7 and 30.
- e. Endothelial cell density at 3 months
- f. Central corneal thickness at day 7, 30 and 90
- g. Best corrected distance visual acuity at day 7, 30 and 90
- h. Intraocular pressure at day 1, 7, and 30
- i. Macular thickness day 7, 30 and 90
- j. Intraoperative complication rate

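### Month 1 and Month 3 are timed from the second eye's surgery while Table 1 implies per-eye visits; the Month 1 window, visit numbering and Visit 5 assessments also conflict and need reconciling

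*Combined protocol and SAP*

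**What the plan says.** **Timing.** Under Visit Schedule (section 3.C.1), Day 1 and Week 1 are timed per eye; Week 1 is 7 days, plus or minus "2 days after surgery each eye". The two later visits have a different anchor. Month 1 is 30 days, plus or minus "7 days postoperative after second eye surgery", and Month 3 is 90 days, plus or minus "15 days postoperative after second eye surgery". Inclusion criterion 6 requires the two operations "within 1 to 15 days between surgeries".

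**Table 1.** The Month 1 column is headed "Visit 4/4A 1-Month 30 ±5 days" and the Month 3 column is labelled 5/5A with ±15 days. The same paired labels head the columns for surgery, Day 1 and Week 1, which the schedule treats per eye. Table 1 states no anchor.

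**Numbering.** The schedule uses Visit 3 for both Week 1 and Month 1 and ends with Month 3 as Visit 4. Measurements and evaluations (3.D), Table 1 and Study endpoint criteria (section 4) all run to Visit 5, and completion is defined by Visit 5.

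**Visit 5 content.** Section 3.D reads "Visit 5: Manifest refraction, best distance corrected visual acuity (BCVA), IOP, slit lamp examination, ultrasound pachymetry, Pentacam macular OCT will be performed", with a fundus examination if needed. Specular microscopy is not named. Table 1 marks it at Visit 5/5A, and endothelial cell density (ECD) at 3 months is secondary endpoint e. For intraocular pressure the conflict runs the other way: it is in the Visit 5 text but unmarked in Table 1.

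**Endpoints.** The late secondary endpoints are named by day, for example "Central corneal thickness at day 7, 30 and 90".

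**The concern.** In a contralateral-eye design each pair supplies its own control, so the two eyes should be compared at a known and similar stage of recovery. With one late visit timed from the second operation, the first eye is always further on by the gap between operations. The first eye is also the one with the worse cataract, so postoperative age, eye order and cataract severity move together. Statistical Analysis (5.B) names no term for order or time.

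The conflicting texts also have practical consequences. Section 4 discontinues patients who fail to meet the visit schedule, and section 9 requires deviations to be documented. Neither can be applied consistently when the Month 1 window has two widths. A coordinator working only from the Visit 5 text would not see the measurement that the 3-month ECD endpoint needs.

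**Working it through.** The plan gives no figure to reproduce here; the check is window arithmetic.

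**Inputs.** Gap between surgeries g = 1 to 15 days (inclusion criterion 6). Month 1 = 30 ± 7 days (Visit Schedule) or "1-Month 30 ±5 days" (Table 1). Month 3 = 90 ± 15 days (both).

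**Formula.** At a joint visit, first-eye day = second-eye day + g.

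| Visit | Second eye | First eye, earliest | First eye, latest |
|---|---|---|---|
| Month 1, ±7 | 23 to 37 | 23 + 1 = 24 | 37 + 15 = 52 |
| Month 1, ±5 | 25 to 35 | 25 + 1 = 26 | 35 + 15 = 50 |
| Month 3, ±15 | 75 to 105 | 75 + 1 = 76 | 105 + 15 = 120 |

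**Can one visit put both eyes in the same window?** Only if g is no more than twice the half-width.
- ±7: g up to 14. At g = 15 the earliest first-eye day is 23 + 15 = 38, beyond 37.
- ±5: g up to 10. At g = 11 the earliest is 25 + 11 = 36, beyond 35.
- ±15: g up to 30, so every allowed gap can be met.

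**Visit held exactly on the nominal day of the second eye.** At day 30 the first eye is at 30 + g. It is past 37 for gaps of 8 to 15 days and past 35 for gaps of 6 to 15 days. At day 90 it is at 91 to 105, inside ±15 for every gap.

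**Window conflict.** If both Month 1 windows are counted from the second surgery, ±7 allows days 23 to 37 and ±5 allows days 25 to 35. Visits on days 23, 24, 36 and 37 comply with one text and deviate from the other.

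**Effect on the device comparison.** Suppose all 40 pairs have gap g, and n pairs have device A in the first eye. The mean age difference between devices is [n·g − (40 − n)·g]/40. It is 0 at 20:20. At 24:16 it is 8g/40 = 0.2g, which is 0.2 days at g = 1 and 3 days at g = 15. No blocking is stated. If randomisation were simple (an assumption), a 24:16 or more uneven split in either direction has probability of about 0.27, and 25:15 or more uneven about 0.15.

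**Endpoints touched.** Those with a day-30 part are d (inflammation), f (corneal thickness), g (acuity), h (intraocular pressure) and i (macular thickness): five of the ten secondary endpoints. ECD (e) is measured at Month 3 only. Both primary endpoints fall outside: day-1 corneal thickness is timed per eye, and lens removal time is intraoperative.

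**The case against.** The strongest reply is randomisation. The first eye is randomised to device and the fellow eye receives the other, so order, cataract severity and the timing offset balance between devices in expectation. A reader might infer from the schedule that one device is systematically assessed later than the other. The documents do not support that. What remains is added within-pair variation and whatever imbalance arises by chance in 40 pairs. This objection stands.

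Other stronger readings also fail:
- *That all the late measures are still changing between weeks 3 and 8.* The Introduction discusses corneal thickness only, and calls the evidence contradictory: recovery by 4 weeks in some reports, increases lasting 6 months or 1 year in others. Nothing is said about the other measures, so the size of any timing effect is unknown.
- *That first eyes will typically be seen at day 52.* That figure joins the latest permitted visit to the longest permitted gap.
- *That Month 3 is equally affected.* Every allowed gap can be accommodated within ±15 days, although a late visit can still take the first eye past day 105.
- *That the 3-month ECD endpoint has no planned measurement.* Table 1 schedules it. The postoperative lists in 3.D are not exhaustive; they do not name cells and flare either.

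It is also fair to say that a joint late visit is a legitimate choice, and that per-eye windows would not equalise ages: two eyes each in window could still differ by 14 days (±7), 10 days (±5) or 30 days (±15). The trial calls itself a pilot. None of this resolves the contradictions between the texts.

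**Conclusion.** The concern holds as an inconsistency in operative schedule rules, with a modest statistical consequence. The anchor, the Month 1 window, the visit numbering and the Visit 5 assessments differ between sections, and no precedence rule is given. Under the visit schedule as written, the eyes of a pair differ by 1 to 15 days in postoperative age at each joint late visit. Some permitted gaps make it impossible for both eyes to be in the Month 1 window together: 15 days under ±7, and 11 to 15 days under ±5.

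The effect is order-related noise and possible chance imbalance in the day-30 parts of endpoints d, f, g, h and i. It is minor at Month 3 and absent from the primary endpoints. The ranges assume a joint visit timed from the second surgery; if the paired columns of Table 1 mean per-eye visits, the systematic offset disappears. How far the offset moves any measurement cannot be derived from the documents.

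**What to change.** 1. Reconcile the Visit Schedule, section 3.D and Table 1: one stated anchor for Months 1 and 3, one Month 1 window, and one visit numbering ending at Visit 5.
2. Give a single Visit 5 assessment list that includes specular microscopy, and settle whether intraocular pressure belongs on it. Endpoint h stops at day 30, so no listed endpoint depends on the latter.
3. If the joint late visit is kept, include eye order in the paired analysis of the late secondary endpoints. This removes the average order and timing difference from the device comparison. The order estimate should not be read as a timing effect, since order also carries cataract severity.
4. Report each eye's actual days since its own surgery, and use them as a covariate in a sensitivity analysis only. With joint visits they are partly collinear with eye order, and hardly separable from it within pairs if the gaps vary little.

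The cost is a short protocol clarification and one extra model term. No additional visits are needed if the joint visit is kept. If per-eye timing is chosen, a separate Month 1 visit is unavoidable only for the gaps that one visit cannot cover.

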### D. Measurements and evaluations

1. Visit 0: Informed consent process will be conducted at this visit. Assessments include best-corrected distance visual acuity (BCDVA, Snellen chart), manifest refraction, intraocular pressure (IOP, Goldman), corneal tomography (Pentacam), ultrasound pachymetry, specular microscopy, macular OCT, slit lamp examination including dilated fundus exam, cataract density and type (LOCS III). Any testing that is part of the site's standard of care preoperative cataract surgery evaluation may be performed prior to the informed consent being signed provided these tests are conducted within 90 days of the surgery and notation of the date performed is entered onto the CRF. The surgeon's standard pre cataract surgery treatment will be used in all his patients

First eye undergoing surgery will be randomized to Group A (Quatera 700) or B (Centurion).

2. Visit 1: The surgeon may use his preferred small incision cataract extraction technique (manual phacoemulsification or laser assisted). The same technique must be used in both eyes. The intraocular lens will be implanted in the bag. The following information will be captured the day of surgery: phaco metrics, lens removal time, duration of surgery, incision size (prior to lens implantation), estimated fluid used, lens implanted and power, target refraction for IOL power implanted, additional surgical procedures, intraoperative complications, and any device deficiencies. Additionally, the surgery will be recorded, and the videos will be analyzed digitally using the Surgery Optimizer and manually using a stopwatch. The surgeon's standard post cataract surgery treatment will be used in all patients.

3. Visit 2: monocular pinhole uncorrected visual acuity (UCVA), slit lamp examination, IOP, ultrasound pachymetry and Pentacam.
4. Visit 3: Manifest refraction, best distance corrected visual acuity (BCVA), IOP, slit lamp examination, ultrasound pachymetry, Pentacam and macular OCT.
5. Visit 4: Manifest refraction, best distance corrected visual acuity (BCVA), IOP, slit lamp examination, ultrasound pachymetry, Pentacam, macular OCT, and dilated fundus exam if deemed necessary by the investigator.
6. Visit 5: Manifest refraction, best distance corrected visual acuity (BCVA), IOP, slit lamp examination, ultrasound pachymetry, Pentacam macular OCT will be performed. Dilated fundus exam to be performed if deemed necessary by the investigator.

All adverse events and complaints will be monitored and recorded at all study visits.

**Table 1.** Visits and Study Assessments

	Visit 0 Screening	Visit 1/1A DOS	Visit 2/2A 1-day	Visit 3/3A 1-week 7 ±2 days	Visit 4/4A 1-Month 30 ±5 days	Visit 5/5A 3-Month 90 ±15 days
Informed Consent	X					
Inclusion/Exclusion	X	X				
Demographics	X					
Past medical & ocular history	X					
Concomitant medications	X					
BCVA Snellen	X					
Pinhole uncorrected distance VA (ETDRS)			X			
Manifest refraction	X			X	X	X
Best corrected distance VA (ETDRS)				X	X	X
Intraocular Pressure (Goldman)	X		X	X	X	
Specular microscopy	X					X
Ultrasound Pachymetry	X		X	X	X	X
Pentacam	X		X	X	X	X
SLE	X		X	X	X	X

Signs of inflammation (cells and flare)	X		X	X	X	X†
Dilated fundus exam	X				X††	X††
Macular OCT	X			X	X	X
Cataract density / type (LOCS III)	X					
Phaco metrics		X				
Lens removal time		X				
Duration of surgery		X				
Incision size		X				
Surgical optimizer		X				
Estimated fluid use		X				
Adverse events	X	X	X	X	X	X

X To be performed as scheduled

† To be performed if cells and flare still present at the 1-month visit

†† To be performed as deemed necessary by the investigator.

BCVA, best corrected visual acuity

ETDRS, Early Treatment Diabetic Retinopathy Study

SLE, Slit lamp exam

OCT, Optical Coherence Tomography

LOCS, The Lens Opacities Classification System

